9.5 Efficacy analysis

9.5.1 Primary efficacy analyses

9.5.1.1 First primary analysis: combined endpoint of infection/inflammation, overgrowth, pain and numbness

The primary analysis of the number of events regarding infection/inflammation, overgrowth, pain and numbness (see definition section 5.2.1) between the two study groups will be analysed with the Mantel-Haenszel two-sided chi-square test at a significance level of 0.0499 on the ITT population between 3 weeks and 1 year.

9.5.1.2 Secondary primary analyses: direct medical costs, based on time for surgical procedures, wound healing and complications

The primary analysis of direct medical costs, based on time for surgical procedures, wound healing and complications (see definition section 5.2.1) between the two study groups will be analysed with two-sided Mann-Whitney U-test at significance level 0.0001 on the ITT population up to one year of follow-up.

9.5.2 Secondary efficacy analysis

All secondary variables given in section 5.2.2 will be analysed and described with the methods given in section 9.4 General statistical methodology. All significance tests will be two-sided and conducted at the 5% significance level.

9.5.3 Tertiary efficacy analysis

All tertiary variables given in section 5.2.3 will be analysed and described with the methods given in section 9.4 General statistical methodology. All significance tests will be two-sided and conducted at the 5% significance level.

9.6 Safety analyses

The loss of implants will be analysed with the Log-rank test between the two groups and illustrated with Kaplan-Meier survival curves.

Adverse Events and Serious Adverse Events will be coded with the MedDRA dictionary and tabulated by PT-code and SOC-code and treatment.

9.7 Analyses of concomitant medications and treatments

Concomitant medications will be coded and tabulated by treatment.

9.8 Demographics and baseline characteristics.

Demographics and baseline characteristics are tabulated and analysed by treatment group according to the general methodology given in section 9.4.

9.9 Interim analysis

No interim analysis planned. In addition to the main analysis at one year, only a follow-up analysis after 3 years is planned.

9.10 Statistical Analysis Plan

A statistical analysis plan (SAP) with detailed statistical analyses specified for all variables and time points will be written and signed before the database lock.

10 Administrative part

10.1 Training

The Sponsor will organise an initiation visit during which the CIP, investigational procedures including the informed consent process, case report form completion and any other matters relating to running the investigation at the site should be discussed and queries clarified.

The principal investigator will ensure that appropriate training relevant to the investigation is given to the medical, nursing and other staff involved at the clinic and that new information of relevance to the performance of this investigation is forwarded to the staff involved.

10.2 Investigational data

10.2.1 Case report form

A paper document for each subject on which information that will be reported to the sponsor is recorded. Specific instructions how to complete the CRF will be provided to the investigator and other site staff. Completed CRFs will be reviewed and signed by an investigator.

10.2.2 Source data

Defined as all the information in original records, certified copies of original records of clinical findings, observations, or other activities in a clinical investigation, necessary for the reconstruction and evaluation of the clinical investigation.

The CRF could be source data and before the initiation of the investigation the principal investigators should together with the monitor complete the template 'Origin of source data' stipulating where source data should be recorded at the investigational site.

10.2.3 Data management

A data management plan will be written that describes the overall data handling process including data validation, clarification of data and the clean file process.

All outstanding questions regarding data should be taken during the clean file meeting. After declaring clean file the data will be locked.

10.3 Archiving

The sponsor and principal investigator shall maintain the investigation documents as required by the applicable regulatory requirements.

10.4 Device accountability

Not applicable since the products are CE marked.

10.5 Quality control

10.5.1 Monitoring

The sponsor will appoint a monitor that will visit sites during the investigation. The monitor will be appropriately trained and informed about the nature of the investigation, ISO 14155:2011 and applicable regulatory requirements.

The monitor will verify the informed consent of participating subject, that the investigational team is adhering to the protocol and that data are accurately recorded in the CRF.

The monitor must have direct access to source data.

10.5.2 Audit

Audits of the clinical investigation may be conducted by the sponsor or third party designated by the sponsor to evaluate compliance with the CIP, written procedures, ISO-14155:2011 and applicable regulatory requirements.

10.6 Clinical Investigation Plan

10.6.1 Deviations from Clinical Investigation Plan

Any deviation from the CIP will be recorded together with an explanation of the deviation. Deviations will be reported to the sponsor, who is responsible for analysing them and assessing their significance. The appropriate ethics committee/institutional review board and regulatory authorities will be informed of any significant protocol deviations.

10.7 Suspension or premature termination

The sponsor may suspend or prematurely terminate either an individual investigation site or the entire clinical investigation for significant and documented reasons. A principal investigator may suspend or prematurely terminate participation in the clinical investigation at the investigation site for which he/she is responsible.

10.8 Publication policy

The result of this study will be published. Authors of the primary publication based on this study must fulfil the criteria defined by the International Committee of Medical Journal Editors (ICMJE).

The primary publication must be published before any secondary publications are submitted for publication.

**Clinical and health economic evaluation with a new Baha
abutment design combined with a minimally invasive surgical
technique**

Protocol No:

CBAS5439

Version:

1.0

Page 6 of 23

1 SCOPE

This SAP intends to answer the questions raised in the protocol. This SAP does not include the Health Economic evaluation at 3 years.

Protocol:

Clinical and health economic evaluation with a new Baha abutment design combined with a minimally invasive surgical technique

Protocol No:

CBAS5439

Version:

1.0

Page 8 of 23

Implant stability		X	X	X	X	X	X	X	X	X
Suture removal			X							
Wound healing			X	X	X	X	X			
Baha installation				X						
Use of sound processor ²					X	X	X	X	X	X
Change of abutment			X	X	X	X	X	X	X	X
Loss of implant			X	X	X	X	X	X	X	X
Holgers index			X	X	X	X	X	X	X	X
Soft tissue thickening/overgrowth			X	X	X	X	X	X	X	X
Visible abutment length			X	X	X	X	X	X	X	X
Aesthetic evaluation surgeon						X		X		X
Aesthetic evaluation incl. pain question (POSAS) ³						X		X		X
Pain ^{2,3}			X	X	X		X			
Numbness			X	X	X	X	X	X	X	X
Use of nicotine ²	X			X		X		X	X	X
Health Utilities Index ²	X						X	X		X
Abbreviated Profile of Hearing Aid Benefit ²	X						X	X		X
Extra visits			X	X	X	X	X	X		
Concomitant treatment			X	X	X	X	X	X		
Concomitant medication			X	X	X	X	X	X		
Device deficiency		X	X	X	X	X	X	X	X	X
Adverse events		X	X	X	X	X	X	X		
ADE									X	X
Health care costs ⁴	X	X	X	X	X	X	X	X	X	X

¹ The time between visits will be calculated from visit 1 (time 0)

² To be completed by subject on questionnaires

³ Pain question included in the POSAS scale

⁴ This is not specified like this in the protocol but added here to clarify that we measure Health care costs related to the procedure throughout the study

2.3 Treatment Groups

Subjects were randomised to either:

- Test group: Minimally invasive surgery and use of a BA400 abutment.
- Control group: Standard surgery and use of a BA300 abutment.

2.4 Sample Size

Sample size calculations were performed for both primary analyses. The significance level of 0.05 is split between the two primary analyses: combined endpoint 0.0499 and direct medical cost 0.0001.

2.4.1 Sample size calculation for the combined endpoint of infection/inflammation, overgrowth, pain and numbness

It is estimated that the distribution of the number of events regarding infection/inflammation, overgrowth, pain and numbness with the traditional surgical procedure and BA300 abutment is as follows; 60% no events, 18% one event, 12% two events, 7% three events and 3% four

Protocol:

Clinical and health economic evaluation with a new Baha abutment design combined with a minimally invasive surgical technique

Protocol No:

CBAS5439

Version:

1.0

Page 9 of 23

events. In order to achieve a power of 80% with the Mantel-Haenszel two-sided chi-square test at significance level of 0.0499 when the distribution of the number of events with the new surgical procedure and new abutment BA400 is as follows; 81% no events, 13% one event, 5% two events, 1% three events and 0% four events 50 statistical evaluable subjects are needed in each group. The sample size calculation is based on 10000 simulated studies.

2.4.2 *Sample size calculation for direct medical costs, based on time for surgical procedures, wound healing and complications*

The power that is achieved if the previously needed 50 statistical subjects in each group are used for the economic evaluation is calculated as follows: From a 12 months prospective follow-up by Hultcrantz¹ the mean time required for surgery was 44.57 (SD 7.41) minutes with skin reduction and 28.14 (SD 3.67) minutes without skin reduction. If a normal distribution of the time required for surgery, 15% infection/inflammation and 15% extra dressings with skin reduction, versus 9% infection/inflammation and 10% extra dressings without skin reduction, a power of more than 99% with the two-sided Mann-Whitney U-test at a significance level 0.0001 would be achieved. The sample size calculation is based on 10000 simulated studies.

In order to compensate for a drop-out rate of 5% we needed to randomize 53 subjects to each group.

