9.2 Sample size calculation

Sample size calculations are performed for both primary analyses. The significance level of 0.05 will be split between the two primary analyses: combined endpoint 0.0499 and direct medical cost 0.0001.

9.2.1 Sample size calculation for the combined endpoint of infection/inflammation, overgrowth, pain and numbness

For a definition of first primary endpoint, see section 5.2.1. It is estimated that the distribution of the number of events regarding infection/inflammation, overgrowth, pain and numbness with the traditional surgical procedure and BA300 abutment is as follows; 60% no events, 18% one event, 12% two events, 7% three events and 3% four events. In order to achieve a power of 80% with the Mantel-Haenszel two-sided chi-square test at significance level of 0.0499 when the distribution of the number of events with the new surgical procedure and new abutment BA400 is as follows; 81% no events, 13% one event, 5% two events, 1% three events and 0% four events we need 50 statistical evaluable subjects in each group. The sample size calculation is based on 10000 simulated studies.

9.2.2 Sample size calculation for direct medical costs, based on time for surgical procedures, wound healing and complications

For a definition of the second primary endpoint see section 5.2.1. The power that is achieved if the previously needed 50 statistical subjects in each group are used for the economic evaluation is calculated as follows, From a 12 months prospective follow-up by Hultcrantz² the mean time required for surgery was 44.57 (SD 7.41) minutes with skin reduction and 28.14 (SD 3.67) minutes without skin reduction. If a normal distribution of the costs time required for surgery, 15% infections/inflammations, 15% extra dressings with skin reduction, 9% infections/inflammations and 10% extra dressings without skin reduction, with a power of more than 99% with the two-sided Mann-Whitney U-test at a significance level 0.0001 would be achieved. The sample size calculation is based on 10000 simulated studies.

In order to compensate for a drop-out rate of 5% we need to randomize 53 subjects to each group

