5 STATISTICAL METHODOLOGY

5.1 General Methodology

Continuous variables will be presented with Mean, Standard deviation (SD), 95% confidence interval (CI), Median, Min, Max and number of measures for both treatment groups and categorical variables will be presented with number and percentage.

Information about the methods used for the statistical testing can be found in the paragraphs below.

The primary analyses will be performed on the ITT population and the secondary and tertiary efficacy analyses will be performed on ITT and PP populations. The exploratory analyses are only performed for ITT population. Safety analyses will be performed on the safety population.

STATISTISKA KONSULTGRUPPEN		Statistical Analysis Plan	
Protocol: Clinical and health economic evaluation with a new Baha abutment design combined with a minimally invasive surgical technique		Protocol No: CBAS5439	
		Version: 1.0	Page 16 of 23

In case of significant amount of missing data, sensitivity analyses will be performed. Imputations will be made in the most appropriate way and the techniques used will be similar in the two groups. In case of disagreement between relevant parties, an independent expert will be consulted to ascertain that the method of imputation does not benefit or inhibit one group over the other.

The significance level of 0.05 will be split between the two primary analyses: combined endpoint 0.0499 and direct medical cost 0.0001. All other tests will be two-tailed and conducted at 0.05 significance level. All analyses will be performed by using SAS® v9.4 (Cary, NC).

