7 CHANGES OF ANALYSIS FROM PROTOCOL

The primary economical variable is defined as the following in the protocol:

Protocol:

Clinical and health economic evaluation with a new Baha abutment design combined with a minimally invasive surgical technique

Protocol No:

CBAS5439

Version:

1.0

Page 21 of 23

“direct medical cost associated with the surgery (time to perform surgery, number of wound dressings sessions and cost to treat complications)”

It is now changed to be able to include more costs and is now defined as:

“direct medical cost associated with the surgery (all health care costs, incurred, related to the procedure)”

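### The cost primary stays at a fixed 0.0001 with no alpha passed on, and its stated power was not updated for the wider SAP cost definition

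*SAP*

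**What the plan says.** Protocol 9.2 sets the rule: "The significance level of 0.05 will be split between the two primary analyses: combined endpoint 0.0499 and direct medical cost 0.0001". Protocol 9.5.1.2 applies it to cost as a "two-sided Mann-Whitney U-test at significance level 0.0001 on the ITT population up to one year of follow-up". SAP 2.4 repeats the split, "combined endpoint 0.0499 and direct medical cost 0.0001", as does SAP 5.1, which adds only "All other tests will be two-tailed and conducted at 0.05 significance level". Neither document gives a testing order or a rule for reusing alpha.

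The cost power in SAP 2.4.2 comes from Protocol 9.2.2. Its inputs are surgery times of "44.57 (SD 7.41) minutes with skin reduction and 28.14 (SD 3.67) minutes without skin reduction", event rates of "15% infection/inflammation and 15% extra dressings with skin reduction", and 9% and 10% for the same two events without skin reduction. With 50 per group the SAP states "a power of more than 99% with the two-sided Mann-Whitney U-test at a significance level 0.0001 would be achieved".

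On the cost endpoint, SAP section 7 says "It is now changed to be able to include more costs" and redefines it as all health care costs related to the procedure. SAP 4.2.2.1 lists surgery time, type of anaesthesia, hospital days, extra visits by staff type and duration, materials and concomitant therapy. It says that the list is not exhaustive.

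**The concern.** Protocol 9.1.1 names cost as one of two primary aims. Under the fixed split, cost must reach p below 0.0001 even when the clinical primary has succeeded. A cost p-value of 0.001 would then be a failed primary aim, while the 0.0499 already earned goes unused.

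Such a strict level is harmless if cost power is near 100%, and the stated figure suggests that it is. But that figure describes a cost built from three inputs. The SAP endpoint has more sources of between-patient variation, and SAP 4.2.2.2 expects costs to differ between centres. If that variation is large next to the surgery-time difference, 0.0001 could decide the result of the second primary.

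**Working it through.** **Inputs from the documents.** Surgery time 44.57 (SD 7.41) vs 28.14 (SD 3.67) minutes; event rates 15%/15% vs 9%/10%; 50 evaluable per arm; levels 0.0499 and 0.0001; combined-endpoint distributions 60/18/12/7/3% vs 81/13/5/1/0%.

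**Assumed.** The documents give no unit costs, so added costs are expressed in surgery-minute equivalents.

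**Step 1: reproduce the plan's figures.**
- Alpha: 0.0499 + 0.0001 = 0.05.
- Surgery-time difference: 44.57 − 28.14 = 16.43. Root-mean-square SD: √((7.41² + 3.67²)/2) = 5.85. Standardised difference: 16.43/5.85 = 2.81.
- Simulated two-sided Mann-Whitney test at 0.0001: surgery time alone gives about 100%. Adding the infection and dressing events, costed at 10 to 300 minute-equivalents each, gives 99.0% to 100%. The stated figure is confirmed for its model.
- Simulated Mantel-Haenszel test for the combined endpoint at 0.0499: 80.7%, against 80% stated.

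**Step 2: what 0.0001 demands.** The standardised difference needed for 80% power with 50 per arm is (z₁₋α/₂ + z₀.₈) × √(2/50):
- at 0.0001: (3.891 + 0.842) × 0.2 = 0.95, or 0.97 allowing for Mann-Whitney efficiency of 0.955;
- at 0.05: (1.960 + 0.842) × 0.2 = 0.56, or 0.57.

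With a difference of 16.43, the total cost SD at 0.0001 can be at most about 16.43/0.97 = 16.9 minute-equivalents. Simulation puts the limit slightly lower, near 16.

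**Step 3: range for the wider endpoint.** These are simulated Mann-Whitney tests, 50 per arm, on surgery time plus an added cost. The added cost is equal in both arms except in the last row.

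| Assumed added cost (minute-equivalents) | Power at 0.0001 | Power at 0.05 |
|---|---|---|
| Normal, SD 10 | 99.7% | 100% |
| Normal, SD 15 | 79% | 99.7% |
| Normal, SD 20 | 40% | 97% |
| Normal, SD 30 | 8% | 74% |
| 100 in 10% of patients (SD 30) | about 100% | 100% |
| 100 in 20% of patients (SD 40) | 97% | about 100% |
| 100 in 30% of patients (SD 46) | 84% | 99.9% |
| Normal, SD 20, plus 5 favouring test | 81% | 99.9% |

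The SDs in the sparse rows are 100 × √(p(1 − p)). If infection and dressing events are also costed at 30 each, the four equal-arm normal rows at 0.0001 become about 92%, 68%, 40% and 12%. A right-skewed added cost (lognormal, coefficient of variation 1) on top of those events gives 75% at mean 20 and 45% at mean 30.

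**Step 4: what passing alpha on would add.** Cost power = P(clinical succeeds) × power at 0.05 + P(clinical fails) × power at 0.0001, with 80.7% clinical power and independence assumed:
- SD 15: 0.807 × 0.997 + 0.193 × 0.79 = 96%, against 79%;
- SD 20: 0.807 × 0.97 + 0.193 × 0.40 = 86%, against 40%;
- SD 30: 0.807 × 0.74 + 0.193 × 0.08 = 61%, against 8%.

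In the other direction almost nothing changes: the clinical critical value moves from 1.9608 to 1.9600.

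**The case against.** The best defence has four parts.

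1. **The split is valid.** It sums to 0.05, and not recycling is a choice about efficiency. This stands in full. A reader might infer inflated type I error from the odd split, and the documents do not support that.
2. **The widening is smaller than section 7 suggests.** Protocol 7.3.3 already recorded attending staff, type of anaesthesia, extra dressing visits with duration and materials, and all resources for complications including concomitant medication. SAP 4.2.2 also still names the three protocol components. This largely stands. Hospital days and the open-ended list are the clearest additions, and part of the mismatch between power model and endpoint was already in the protocol.
3. **Added spread need not cost power.** Complication costs fall on a minority of patients, and a rank test is little affected by sparse large costs. The table shows this: at the same SD of 30, power is 8% for normal spread and about 100% for sparse costs. The trial also expects lower complication costs in the test arm, which would offset noise. This stands, so one cannot conclude that cost is underpowered.
4. **The gains in step 4 assume independence**, although complications enter both primaries. This stands too; they are illustrations.

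The defence does not explain why the power figure was carried over after the endpoint changed, or what is gained by discarding alpha.

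**Conclusion.** The point holds in two limited parts. First, the fixed split is valid but less efficient than a rule that passes alpha on, and the loss falls almost wholly on the cost primary. Second, the cost power of more than 99% is correct for surgery time, infection/inflammation and dressings, but nothing in the documents supports it for the endpoint as the SAP now defines it.

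The size of any power loss cannot be derived from the documents. It depends on the spread, shape and direction of the added costs. It is negligible if the spread is about 10 minute-equivalents or less, if the costs are confined to roughly a tenth of patients, or if they clearly favour the test arm. It is severe if broad spread of 20 or more affects most patients equally in both arms. A reader might infer that the second primary is likely to fail, but that needs the unfavourable end of this range.

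**What to change.** 1. **Specify weighted Holm in SAP 5.1.** Test the combined endpoint at 0.0499 and cost at 0.0001. If either is significant, test the other at 0.05. If both nulls are true, a false rejection needs one of the two initial tests to reject, with probability at most 0.0499 + 0.0001 = 0.05. If only one null is true, it is never tested above 0.05. Every rejection under the present rule is kept.
2. **Correct SAP 2.4.2.** Either say that the power applies to surgery time, infections and dressings only, or recompute it for the section 7 endpoint with stated unit costs and an assumed spread and shape.
3. **Name the one cost p-value that enters the rule.** SAP 5.7.1.2 offers a t-test, a bootstrap interval and a Mann-Whitney test without restating the level, and SAP 4.2.2.2 produces one costing per country.

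Items 1 and 3 must be fixed before database lock and before anyone has seen comparative results, which matters more because the trial is open. The cost is a few sentences, plus a short simulation if the power is recomputed. No extra patients or data are needed.

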3 STUDY POPULATIONS

3.1 Definition of Study Populations

3.1.1 *Intent-to-Treat Population (Full Analysis Set)*

The Intent to Treat population (ITT) consists of all randomised patients with at least one follow-up measurement from visit 3 Day 10 and onward.

3.1.2 *Per-Protocol Population*

The Per Protocol population (PP) will include subjects that have completed the investigation according to the protocol. Subjects that were incorrectly randomised or were considered major protocol violators should be removed from the PP population.

3.1.3 *Safety Population*

The safety population consists of all surgically treated patients, grouped after surgical procedure.

